#### Number of subjects planned:

The trial will apply an adaptive group sequential design with one interim analysis that will be performed on the subjects randomised in Year 1 (N=555). In case the decision is taken to progress the study to a second season after the interim analysis, the sample size will be recalculated.

**Study period:** Estimated first subject enrolled (Q3/2023) and last subject last visit (Q3/2024). The end of study (EoS) is defined as the date of the last 6 months telephone follow-up call of the last subject in the study.

Protocol: PQGrass306

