#### **Overall Design (Brief Summary):**

This is a multi-centre, randomised, parallel group, double-blind, placebo-controlled clinical trial to confirm the efficacy and safety of the optimal effective dose of PQ Grass (27600 SU). The trial will have an adaptive group sequential design with one planned interim analysis.

Subjects will be assigned in a ratio of 1:1 (PQ Grass:Placebo) with treatment course to be completed prior to the onset of the grass pollen season (GPS):

- **PQ Grass:** 6 injections of PQ Grass (900, 2700, 6000, 6000, 6000, 6000 SU sequentially) *or*
- **Placebo:** 6 injections of placebo

The study includes 4 periods, encompassing 11 visits to the study site and at least 2 follow-up telephone calls. Subjects will be provided with enough relief medication to cover them through this period by the study site.

**Period 1** (Screening [Visit  $1 \pm \text{Visit 1a}$ ]): This includes the screening visit at which subjects' eligibility for the clinical trial will be assessed.

**Period 2** (Randomisation and treatment [Visit 2 to Visit 7]): At Visit 2, subjects will be randomly allocated in a randomisation ratio of 1:1 to the active treatment (PQ Grass) or the placebo treatment group and will receive the first injection.

After Randomization at Visit 2, subjects will thereafter return to the study site at subsequent visits during the treatment period (Visit 3 to Visit 7) to receive the remaining injections. The average duration of the treatment period will be approximately 16 weeks.

Treatment with either 6 injections of active treatment (900, 2700, 6000, 6000, 6000 and 6000 SU sequentially) to achieve a cumulative nominal dose of 27600 SU, or 6 injections of placebo will be administered prior to the onset of the GPS.

**Period 3** During the GPS, subjects will record their allergic rhinitis/rhinoconjunctivitis symptoms and use of relief medications in an electronic diary (eDiary). The symptom and medication scores during the peak GPS and the entire (or truncated) GPS calculated according to the European Academy of Allergy and Clinical Immunology (EAACI) recommendations for the CSMS (primary endpoint) will be compared between the active and placebo treatment groups. The following 4 visits will be performed:

- Visit 8 (pre-GPS)
- Visit 9 ( $\approx$  onset of GPS)
- Visit 10 (during GPS)
- Visit 11 ( $\approx$  end of GPS)

Protocol: PQGrass306

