#### Statistical methods

This is the pivotal Phase III study with PQ Grass. The primary endpoint of the study will be the CSMS averaged over the peak GPS.

The difference in CSMS between PQ Grass and placebo will be evaluated using a linear mixed model. Subjects with missing daily CSMS during the peak GPS will be included in the primary analysis by using multiple imputation methods to impute missing values on a by-day level.

The statistical analysis will be performed using a linear mixed model. In the context of the adaptive design, a 1-sided testing will be used using group sequential Pocock boundaries chosen such that an overall 1 sided type 1 error rate of 2.5% was preserved.

For the interim analysis after Year 1, the 1-sided p-value was therefore to be compared with  $\alpha$  = 0.01419 for a statistically significant superiority of the active treatment over placebo.

The difference between PQ Grass and placebo will be estimated using least squares (LS) means. Two-sided appropriate confidence intervals (CIs) for the difference between treatment groups

[figure not shown]

will be provided. The difference between treatment groups will also be presented in percent relative to the LS mean in the placebo group.

The secondary endpoints will generally be analyzed using a similar statistical approach as the primary endpoint. The statistical hypotheses for the key secondary endpoints will only to be tested in a confirmatory sense if the analysis of the primary endpoint is statistically significant. Multiplicity in the key secondary endpoints will be addressed.

The frequency, relationship and severity of AEs and frequency of premature discontinuations from treatment or study due to AEs will be assessed within each treatment group.

**Adjudication Committee:** Yes **Trial Oversight Committee:** Yes

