## 3.1 Analyses planned and already performed

One interim analysis will be conducted after the grass pollen season (GPS) of the first year (Year 1) is terminated and all subjects treated in Year 1 have completed Period 3 (PreGPS, Onset of GPS, During GPS and End of GPS assessments, including Visit 11).

Based on the results of the interim analysis one of the following 3 scenarios will occur:

- The trial stops for success.
- The trial progresses to Year 2.
- The trial stops for futility.

In case the trial progresses to Year 2 based on the interim result, a recalculation of the sample size will be performed, and the sample size may be adapted.

In case the trial is terminated based on interim analysis results and this decision is documented in writing, the results of the primary analysis will be shared with the Sponsor. Furthermore, group unblinded topline results of efficacy will be prepared and distributed to the Sponsor. As the subjects will continue with the safety follow-up, all personnel involved in the conduct of the trial will stay blinded until the database including safety data has been locked.

In case the trial will continue into Year 2, no unblinding of personnel involved in the conduct of the trial will occur after the interim analysis. After all subjects enrolled in Year 2 have completed Period 3 (including Visit 11), all data relevant for the efficacy analysis will be locked and group unblinded topline results of efficacy will be generated and distributed to the Sponsor. All personnel involved in the conduct of the trial will stay blinded until the last safety follow-up is performed and all data.

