#### 7.7.1.5. Statistical analysis method

The primary efficacy analysis for this clinical trial will be a comparison of the mean average CSMS during the peak GPS in the PQ Grass versus the placebo group.

The following null and alternative hypotheses will be tested for the primary endpoint, based on all subjects who received at least 1 injection of the clinical trial medication, i.e., are included in the FAS (two-sided test):

μ: arithmetic mean of the average CSMS over the peak GPS

The primary efficacy endpoint will be evaluated using a linear mixed model.

The difference between PQ Grass and placebo will be estimated using least squares (LS) means. Two-sided 95% repeated confidence intervals (RCIs) for the difference between treatment groups will be provided at the interim and (if applicable) at the final analysis, which will ensure 95% probability despite calculation at the interim and (if applicable) final analysis.

The difference between treatment groups will also be presented in percent relative to the LS mean in the placebo group, and the CI will be calculated by approximating the SE using the delta method.

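### The SAP reports only the unadjusted LS-mean difference although the trial can stop for success after Year 1, so the reported effect tends to be too large when averaged over both outcomes

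*SAP*

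**What the plan says.** The Protocol (Statistical methods) uses "group sequential Pocock boundaries chosen such that an overall 1 sided type 1 error rate of 2.5% was preserved". At Year 1 the one-sided p-value is compared with "0.01419 for a statistically significant superiority of the active treatment over placebo". SAP 3.1 lists three outcomes of the interim analysis: "The trial stops for success", continuation to Year 2, or a stop for futility. On continuation, the Protocol (Number of subjects planned) says: "In case the decision is taken to progress the study to a second season after the interim analysis, the sample size will be recalculated".

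On estimation, SAP 7.7.1.5 says: "The difference between PQ Grass and placebo will be estimated using least squares (LS) means". The same section:

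- gives the absolute difference a 95% repeated confidence interval at each look;
- expresses the difference as a percent of the placebo LS mean, with a delta-method interval that is not described as repeated.

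The released text mentions no point estimate adjusted for the sequential design and no caveat on overestimation after an early stop.

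**The concern.** The plan accounts for the two looks in the test and in the interval for the absolute difference, but not in the point estimate. A trial that stops because its test statistic crossed a boundary has been selected partly for favourable chance. A repeated interval is wider than an ordinary one, but it has the same centre.

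At stake is the size of the CSMS reduction, in absolute and percent terms. These are the figures that readers of a pivotal trial will take away, and a Year 1 success is one of the planned outcomes. An adjusted estimate chosen after seeing such a stop would carry little weight, so it has to be specified beforehand.

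**Working it through.** **Inputs from the documents:** overall one-sided level 0.025, Pocock boundaries, interim level 0.01419 (Protocol, Statistical methods); 555 subjects in Year 1 (Protocol, Number of subjects planned); one interim analysis (Protocol, Overall Design).

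**Assumptions, because the released text gives no figure:** information fraction t, power, planned size kept in Year 2, no futility stop.

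**1. Reproduce 0.01419.** The boundary is c = Φ⁻¹(1 − 0.01419) = 2.192. With corr(Z1, Z2) = √t, a constant two-look boundary solves P(Z1 > c or Z2 > c) = 0.025. The local level is 0.01414 at t = 0.40, 0.01419 at 0.41, 0.01424 at 0.42 and 0.01469 at 0.50. Solving exactly gives t = 0.409, a total of 555/0.4094 ≈ 1,356. If the level came from Pocock-type alpha spending, 0.025·ln(1 + (e − 1)t) = 0.01419 gives t = 0.445, a total of about 1,248. This is one equation in one unknown, so it infers t and does not check it.

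**2. Bias of the unadjusted estimate at t = 0.41.** Take the effect as placebo minus active, scaled so that the estimate is Z1/√t at a stop and Z2 otherwise, with true value d. Let m = d√t and p = P(stop) = Φ(m − c). The mean estimate divided by the truth is:

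- given a stop: 1 + φ(c − m)/(p·m)
- over both outcomes: 1 + (1 − t)·φ(c − m)/m
- given continuation: (overall − p × given stop)/(1 − p)

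| | 80% overall power | 90% overall power | 90% interim power |
|---|---|---|---|
| d | 2.973 | 3.421 | 5.425 |
| m | 1.904 | 2.190 | 3.474 |
| p | 0.387 | 0.499 | 0.900 |
| φ(c − m) | 0.3827 | 0.3989 | 0.1755 |
| Given a stop | 1.52 | 1.365 | 1.056 |
| Both outcomes | 1.119 | 1.107 | 1.030 |
| Given continuation | 0.866 | 0.851 | 0.79 |

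For 80% power: 0.3827/(0.387 × 1.904) = 0.52; 0.59 × 0.3827/1.904 = 0.119; (1.119 − 0.387 × 1.52)/0.613 = 0.866. A simulation of 2,000,000 trials at 90% power gave 1.364 given a stop and 1.108 overall.

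**3. Sensitivity.**

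- *Information fraction:* at t = 0.445 the overall ratios are 1.109 and 1.097 (80% and 90% power), and 1.475 and 1.327 given a stop. For t from 0.30 to 0.50 the overall ratio runs from 1.15 down to 1.08.
- *Futility:* the rule is not public. An illustrative stop at Z1 below 0.5 or below 1.0 lowers the overall excess from 12% to 7% or 4% (80% power) and from 11% to 8% or 5% (90% power).
- *Percent scale*, assuming a placebo mean of 1.5 and SD of 1.0 to 1.2: 1.09 overall and 1.33 given a stop at 50% interim power; 1.02 and 1.04-1.05 at 90% interim power.

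**4. What an adjustment does.** The Whitehead estimate is the value of d whose expected unadjusted estimate equals the one observed. At t = 0.41 its share of the unadjusted difference at a Year 1 stop is:

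| Z1 | 2.19 | 2.5 | 3.0 | 3.5 | 4.0 | 4.5 |
|---|---|---|---|---|---|---|
| Share | 0.895 | 0.906 | 0.935 | 0.967 | 0.987 | 0.996 |

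At t = 0.445 the shares run from 0.901 to 0.996. A median-unbiased estimate under stage-wise ordering equals the unadjusted one at a first-look stop, so it would change nothing there. With Whitehead at a stop and the stage-wise median-unbiased estimate at the final analysis, the overall excess falls from 11-12% to about 2-3%, with slightly lower root mean squared error. Given a stop, the average is still 1.42 (80% power) or 1.28 (90% power) times the truth.

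**The case against.** **The omission may not be real.** SAP 7.7.1.6 is very short in the released text, subsection numbers are skipped, and a textbook on adaptive designs is listed without a visible citation. An adjusted estimate could sit in text that was not released. This stands, and the point is limited to the released text.

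**The size is selective.** Effect, SD and power are not given, and a plan that asks whether a second season is needed may have high interim power, in which case the bias is small. This stands as a limit on size. The 90% interim-power case is demanding, though: with d = 5.425, Z2 alone would exceed c with probability Φ(5.425 − 2.192) = Φ(3.23), above 99.9%.

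**The adjustment is partial.** It leaves most of the conditional excess after a stop. After continuation it moves the average further down, from 0.87 to 0.79 of the truth at 80% power and from 0.85 to 0.76 at 90%. This is correct: the adjustment targets bias averaged over both outcomes. The final-stage version must also suit a recalculated sample size.

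**It is a preference, since test and interval are valid.** Their validity is accepted. But a reduction in average bias from 11-12% to 2-3% at almost no cost is a concrete gain.

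A reader might go further and infer that whatever benefit is reported will be biased upwards. The documents do not support that: if the trial continues, the final estimate is on average too low. Nor do they state 41% as the planned fraction.

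**Conclusion.** The point holds as a cheap improvement to estimation. It is not a fault in error control. In the released text the only effect estimates are unadjusted, in a design that can stop early for success, and averaged over both outcomes they tend to be too large.

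The main figures (11-12% overall, 37-52% after a Year 1 stop, 13-15% too low after continuation) rest on t of about 0.41, 80-90% overall power, no futility stop and no change in sample size. The size is uncertain: it falls to about 3% overall and 6% after a stop at 90% interim power, and a futility stop lowers the overall figure.

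A reader might take 37-52% as the error to expect in the published result, or as something the adjustment would remove. Neither follows. It is an average over trials that stop, under assumed power, and most of it remains after adjustment.

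**What to change.** Add to SAP 7.7.1.5, as a pre-specified supportive result beside the LS-mean difference and on both the absolute and percent scales:

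- **Year 1 success stop:** a Whitehead bias-adjusted estimate, with the planned information fraction stated. It is about 10% smaller than the unadjusted difference at the boundary and under 2% smaller from Z of about 4.
- **Final analysis:** a median-unbiased estimate matched to the adaptive test actually used, so that it remains valid after sample size recalculation.
- **One sentence of interpretation:** the adjustment addresses bias averaged over both outcomes and does not remove the conditional overestimation after an early stop.

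The test, the boundary and the repeated confidence interval stay as they are. The cost is a paragraph in the SAP, a short program, and a second, somewhat less favourable effect size in the report. If unreleased text already specifies such an estimate, a cross-reference in 7.7.1.5 closes the point.

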#### 7.7.1.6. Adaptive design and interim analysis

The interim analysis will be performed based on the subjects randomised in Year 1. Objectives of this interim analysis include an evaluation whether a second recruitment season for the remaining subjects is actually required, and an evaluation whether the planned sample size is adequate or should be adapted.

## 7.7.2 Key secondary efficacy analyses

The key secondary efficacy endpoints will only be addressed with statistical hypothesis tests if the primary endpoint shows a statistically significant difference between treatment groups. Multiplicity in the key secondary endpoints will be addressed with the Fallback method. The full 5.0% two-sided alpha for the Fallback method will be distributed across the 8 key secondary endpoints. If the preceding hypothesis test is not significant, subsequent tests will be performed at the aforementioned alpha-level. If tests are significant, the alpha is added to the subsequent hypothesis test.

All p-values for the analyses of key secondary endpoints will be presented without adjusting for multiplicity. The evaluation whether the null hypotheses can be rejected or not will be done based on the raw p-values. Cls (for example for the LS means) will also be presented in an explorative way, i.e., two-sided 95% Cls will be presented without a formal multiplicity adjustment.

This document is based on

BM-04-DFC01

Document Standard for Statistical Analysis Plan (SAP) v 14.0

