**Table 1 Objectives and endpoints** 

Table 1 Objectives and endpoints Objectives	Endpoints
Primary Efficacy	
To evaluate the efficacy of PQ Grass 27600 SU in subjects with grass pollen induced seasonal allergic rhinitis (SAR) and/or rhinoconjunctivitis based on symptoms and medications.	Combined Symptom and Medication Score (CSMS) averaged over the peak grass pollen season (GPS).
Secondary Efficacy	
To evaluate the potential of PQ Grass 27600 SU to reduce symptom burden and the need for medication use.	The number of well days during the peak GPS.
To evaluate the quality of life.	Rhinoconjunctivitis quality of life questionnaire with standardised activities (RQLQ(S)) measured within the peak GPS.
To evaluate the effect of PQ Grass 27600 SU on IgG4.	Serum grass-specific IgG4 at Visit 7 compared to baseline.
To evaluate the treatment effect of PQ Grass on the CSMS over the entire GPS.	CSMS averaged over the entire (or truncated) GPS.
To evaluate the treatment effect of PQ Grass on the daily Symptom Score (dSS) and daily	dSS component of the CSMS averaged over the peak GPS and entire (or truncated) GPS.
Medication Score (dMS) components of the CSMS over the GPS.	dMS component of the CSMS averaged over the peak GPS and entire (or truncated) GPS.
Safety	
To evaluate the safety and tolerability of PQ Grass in subjects with grass pollen induced SAR	Frequency, severity and relationship of adverse events (AEs) to treatment.
and/or rhinoconjunctivitis.	Frequency of AEs leading to premature discontinuation from treatment or clinical trial.
	Frequency of adverse events of special interest (AESIs).
	Changes in clinical laboratory values (serum chemistry, haematology and urinalysis) between screening and Visit 11.
	Changes in vital signs at all treatment visits.

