## 7.7.1.2. Daily Combined Symptom and Medication Score

The daily CSMS is the sum of the daily Symptom Score (dSS) component of the CSMS and the daily Medication Score (dMS) component of the CSMS calculated from the data recorded in the eDiary.

The dSS is calculated as the sum of the severity of conjunctival symptoms (2 items) and nasal symptoms (4 items) divided by 6 for each subject and day (see Table 9).

The severity of symptoms is recorded on a 4-point severity scale:

- 0 = No symptoms,
- 1 = Mild symptoms
   (sign/symptom clearly present, but with minimal awareness and easily tolerated),
- 2 = Moderate symptoms
   (definite awareness of sign/symptom that is bothersome but tolerable), and
- 3 = Severe symptoms
   (sign/symptom that is hard to tolerate; causes interference with activities of
   daily living and/or sleeping).

Table 9: Conjunctival and nasal symptoms of the CSMS

Conjunctival Symptoms	Itchy/red eyes *
	Watery eyes
N 10 1	Blocked nose
Nasal Symptoms	Runny nose

Itchy nose
Sneezing

\* Maximum of single items "Itchy eyes" and "Red eyes" is used for analysis.

The dMS is equal to the raw score assigned to each subject and day for the medication with the highest step taken that day.

Thereby, medication is rated on a 4-point scale:

- 0 = No relief medication used,
- 1 = Oral antihistamine/Ocular antihistamine (Step 1 medication),
- 2 = Intranasal corticosteroids (Step 2 medication) with Step 1 medication(s), and • 3 = Oral corticosteroids (Step 3 medication) with Step 1 and Step 2 medications.

A subject will be assigned 1 score (i.e., 1, 2 or 3) per day based on at least 1 dose of the medication of the highest step taken that day, regardless of if more than 1 medication from different steps has been taken. In case, no relief medication is taken, a score of 0 is assigned. For example, a subject taking antihistamine eye drops (Step 1), an antihistamine tablet (Step 1) and intranasal corticosteroids (Step 2) on the same day would be allotted a score of 2 for the Step 2 medication taken.

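### Do the key secondary endpoints need their own group sequential levels, because the primary result decides at which look they are tested?

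*SAP*

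**What the plan says.** SAP 7.7.2 tests the key secondary endpoints only after a significant primary result. On the level it says: "The full 5.0% two-sided alpha for the Fallback method will be distributed across the 8 key secondary endpoints". Alpha from a rejected hypothesis passes to the next one, so the last endpoint can hold the whole 5% if the seven before it are rejected. On the decision rule it says: "The evaluation whether the null hypotheses can be rejected or not will be done based on the raw p-values". The visible text gives neither the order nor the shares, and no level per look.

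The primary has two possible looks. SAP 3.1 gives as one interim outcome: "The trial stops for success". The protocol's Statistical methods section sets Pocock boundaries at an overall one-sided 2.5% and continues: "For the interim analysis after Year 1, the 1-sided p-value was therefore to be compared with" 0.01419. SAP 7.7.1.5 carries the two looks into the estimation: "Two-sided 95% repeated confidence intervals (RCIs) for the difference between treatment groups will be provided at the interim", and at the final analysis if there is one. In the visible text this protection is described for the primary only.

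Several secondaries are tied to the primary by construction. SAP 7.7.1.2 says: "The daily CSMS is the sum of the daily Symptom Score (dSS) component of the CSMS and the daily Medication Score (dMS) component". The symptom score (dSS), the medication score (dMS) and the entire-season CSMS are all key secondaries.

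**The concern.** Each secondary is tested once, behind a gate, which seems to make a second adjustment unnecessary. That reasoning is incomplete. The primary result chooses the look. If the primary crosses early partly by luck, a correlated secondary shares the luck at that look. If the primary misses at Year 1, the secondary gets its test at the final look instead. A null endpoint thus has two routes to a false benefit claim, and a fixed critical value does not guarantee that together they stay below half of its two-sided level.

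At stake would be a benefit claim on a late-order secondary, called confirmatory, with a one-sided error above the 2.5% that the protocol uses for the primary. The primary itself is not touched.

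**Working it through.** **Inputs from the documents.** Overall one-sided alpha for the primary is 0.025, with a Year 1 level of 0.01419, so c1 = 2.192 (protocol, Statistical methods). The secondary family has 5.0% two-sided over 8 endpoints (SAP 7.7.2), so an endpoint holding everything has k = 1.960.

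**Assumptions.** The information fraction t at Year 1, primary power (87%), the correlation rho with the primary, equal Fallback shares of 5.0%/8 = 0.625%, and no futility stop.

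**The plan's own figure first.** Solve P(Z1 > c or Z2 > c) = 0.025 with corr(Z1, Z2) = sqrt(t). At t = 0.5 the one-sided level is 0.01469. At t = 0.409 it is 0.01419, the stated figure. So 0.01419 fits a constant Pocock boundary at t of about 0.41. Keeping c1 = 2.192 and spending all remaining alpha gives c2 = 2.192 at t = 0.409 and 2.165 at t = 0.5.

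**Single endpoint.** For a null secondary S,

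error = P(Z1 > c1, S1 > k) + P(Z1 ≤ c1, Z2 > c2, S2 > k).

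With rho = 0 this is power × 2.5% = 0.87 × 2.5% = 2.2%. At t = 0.409 and rho = 0.5 the two terms are 2.21% and 0.61%, together 2.83%. The harm side uses the same formula with the sign of rho reversed. Results at 87% power for an endpoint holding the full 5%:

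| rho | benefit side, t 0.409 | benefit side, t 0.5 | benefit + harm, t 0.409 |
|---|---|---|---|
| 0.3 | 2.67% | 2.60% | 4.14% |
| 0.5 | 2.83% | 2.71% | 3.78% |
| 0.7 | 2.82% | 2.67% | 3.27% |
| 0.9 | 2.67% | 2.56% | 2.71% |
| 0.95 | 2.63% | 2.54% | 2.64% |

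The correlation adds error on one side and removes more on the other. As the primary effect grows, the two-sided total approaches 5.0% from below, and it exceeded 5.0% in no setting computed.

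**Smaller shares** (same rho range, t = 0.409). The benefit-side error is 2.3-2.5% on 7/8 of the alpha, 2.0-2.1% on 6/8 and 1.6-1.8% on 5/8. With an equal split, only the eighth endpoint can pass 2.5%.

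**Whole Fallback chain by simulation** (t = 0.41, only the eighth endpoint null, the others with 1 or 1.3 times the primary's effect). The error is 2.1-2.6% at rho 0.5, 2.6-2.8% at 0.7 and 2.7% at 0.9. The eighth endpoint inherits the full 5% in only 25-79% of trials. If the seventh and eighth are both null, any false benefit claim among them occurs in 2.2-2.6%.

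**Which endpoint would be eighth?** Three orders are visible, none stated to be the Fallback order:
- SAP Table 1 ends with dMS (seventh and eighth).
- The protocol's objectives table ends with well days, with dMS sixth and seventh.
- SAP 7.7.2.2 to 7.7.2.6 ends with RQLQ, with dMS no later than fifth.

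For dMS the correlation with CSMS over the same window is (k+r)/sqrt(1+k²+2kr), where k here is the SD ratio dMS/dSS and r the dSS-dMS correlation. With k = 1 it runs from 1/sqrt(2) = 0.71 (r = 0) to 1.7/sqrt(3.4) = 0.92 (r = 0.7). But if dMS does nothing over either window, both late positions are null. Peak days lie inside the entire season, so the two windows should be closely correlated. With that correlation at 0.95 (assumption), any false dMS claim occurs in 1.9-2.5% of trials.

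**Cost of using the primary's boundaries for the secondaries.** The full-share error drops to 1.5-1.6% (1.4-1.6% at t = 0.5). A secondary with 80% power at its present level has mean 1.960 + 0.842 = 2.802. Against 2.192 the margin is 0.610, giving 73%; against 2.165 it is 0.637, giving 74%. Counting the gate (87% primary power, full share, same effect as the primary, rho 0.7), the chance of a confirmed secondary falls from 76% to 70%. O'Brien-Fleming levels cost almost nothing at the final look but cut 80% power to about 30-44% if the trial stops at Year 1.

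**The case for a change.** The best case for acting is that the mechanism is sound and the trial is pivotal. The secondaries overlap with the primary by design, and each candidate for last place other than IgG4 reflects the same symptoms and medication use. The excess also grows when the primary effect is weaker. For an endpoint already holding the full 5% at t = 0.41, the maximum is 2.9% at rho 0.5 (75% primary power), 3.1% at 0.7 (47% power) and 3.6% at 0.9 (19% power). Counting the whole chain, with earlier secondaries sharing the primary's effect and t = 0.43, rho 0.9 still gives 2.9% at 65% power. And stating a level per look would take only a few sentences.

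What stands is the mechanism and the direction. The larger maxima have little bearing here, because they suppose seven earlier rejections in a trial with a poor chance of success on its primary. The yardstick is also borrowed: 7.7.2 sets a two-sided level, and the visible hypotheses in 7.7.2.2 and 7.7.2.3 are two-sided.

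Nor can the silence on looks be read as a decision. 7.7.2 refers back to an alpha level that no visible sentence sets, and the numbering passes from 7.7.2 to 7.7.2.2, so the shares, order and levels may sit in unpublished text. The protocol adds that secondaries are generally analysed much as the primary is, and 7.7.2.2 repeats the primary analysis for the entire-season CSMS. Either could carry the two-look treatment over.

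**Conclusion.** The concern is correct as theory and too small to call for a change. The stated 5.0% two-sided level holds for any single endpoint. Against the one-sided 2.5% borrowed from the primary, the excess is at most about 0.3 percentage points. It arises only for a truly null endpoint in eighth place that has inherited all the alpha. That figure rests on an equal split, 87% primary power, t of 0.41 to 0.5 and rho of 0.3 to 0.95, none of which the documents give. At rho 0.5 the whole chain can stay below 2.5%.

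The available remedies overshoot. The primary's boundaries take the error well under the target at a cost of 6 to 7 points of power, and O'Brien-Fleming levels give up much more at a Year 1 stop. Statisticians could reasonably choose either way. What remains is a detail, namely which level applies at which look; on the visible text an analyst would apply the Fallback share at the look where the primary succeeds.
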